1. BACKGROUND AND RATIONALE

Prolonged bed rest, physical inactivity and mechanical unloading is associated with health deficits and functional impairment due to muscle atrophy and loss of muscle function [1]. With a persistency beyond the acute period of inactivity accompanied by long recovery periods [2], physical deconditioning has gained socioeconomic importance in contemporary societies, increasingly raising scientific debates about time courses and underlying mechanisms [3]. Studies in adults documented that skeletal muscle size and function are already reduced after a few days of bed rest [4] and continue to decline with the length of exposure [5].

To intervene, early physical therapy intervention has been initiated in hospitalized patients to increase mobility and reduce muscle weakness from immobility. However, in certain cases, physiotherapy may not be possible due to patient's illness or other circumstances such as isolation due to their medical condition. Haematology patients undergoing induction chemotherapy or stem cell transplant are kept under neutropenic precautions. This includes being isolated in their hospital room for the duration of their treatment which usually lasts 4-6 weeks. At the same time, these patients have limited physiotherapy intervention due to medical reasons (fever, thrombocytopenia, anaemia), compounding their risk for physical deconditioning. Time and again, the post hospitalisation, these previously fit patients are now in a deconditioned state. As the next cycle of treatment begins within the next 10 days, there is little time for the patients to undergo rehabilitation therapy before the next treatment cycle begins and the patient suffers from further deconditioning leading to a vicious cycle. Once treatment is completed, patients are usually deconditioned and the need for rehabilitation prolongs recovery. There is an economic impact as patients need further use of hospital services. There is no current active intervention to prevent such deconditioning in previously fit patients.

Immobilisation also compromises systemic metabolic balance in association with depressed mitochondrial respiration [6]. One manner in which muscle mitochondrial function influences whole-body metabolism is via actions of the muscle secretome [7]. In response to activity dependent activation of mitochondrial respiration, skeletal muscle secretes into the systemic circulation a myriad of regenerative, inflammation and metabolic regulatory factors [7]. Immobilization-induced ectopic accumulation of adipose tissue into muscular and extramuscular sites is associated with increased circulating levels of toxic lipid metabolites, such as the palmitate-derived ceramides. Ceramides are fatty acid derivatives of sphingoid bases, and formed not only through the de novo biosynthetic pathway, but also from the degradation of glycosphingolipids (GSLs) and ceramide-1-phosphate. Ceramides are powerful tumour suppressors that regulate cell proliferation, differentiation, senescence, and apoptosis, which have attracted tremendous attention in combination therapy for cancer treatment [8, 9]. Chemotherapeutic drugs, cytotoxic drugs, hypoxia microenvironment, malnutrition, radiotherapy and hyperthermia can promote the apoptosis of tumour cells by promoting the activity of ceramide synthesis related enzymes and increasing the level of intracellular ceramide [10-12].

Recent studies have shown that the intervention in ceramide production and metabolism will have a significant effect on the treatment of cancer, indicating that ceramides are signal molecules, and have efficiencies of anti-proliferative and pro-apoptotic [13, 14]. These findings raise considerable interest in targeting ceramide metabolism pathways for cancer therapy. Brief exposures to pulsed electromagnetic fields (PEMFs) were previously shown capable of promoting *in vitro* [15] and *in vivo* [16] murine myogeneses via the activation of a calcium-mitochondrial axis promoting mitochondriogenesis, oxidative muscle maintenance, systemic metabolic balance, enhanced fatty acid oxidation as well as produced microbiome shift characteristic of leanness [16]. The implicated PEMF-induced calcium pathway pertained to that mediated by the Transient Receptor Potential Canonical 1 (TRPC1) channel commonly implicated in load-bearing oxidative muscle development and linked to PGC-1 α transcriptional pathways underlying mitochondrial mitohormetic responses

[16]. Studies carried out in senior in the community have demonstrated its effectiveness in increasing skeletal muscle mass and decreasing body fat mass as well as increasing their functional aptitude. PEMFs exposure demonstrated inhibition of growth, migration and invasiveness in breast cancer cells and in treated mice [17].

Klotho and HTA1 has been shown to inhibit the in vitro growth of breast cancer cells [18] and both of these candidates are downregulated in several cancers in correlation to cancer severity [19, 20]. The PEMF induced secretion of both Klotho (and HTA1) may hence serve as manner to manage cancer progression.

This study aims to examine a direct benefit of PEMFs on the patient's muscle mass and physical functioning and indirect benefit on the patient's cancer management. If this pilot study is successful in demonstrating our specific aims, we plan to extend the study to other patient populations specifically targeting the elderly cancer patients.

1.1. General Introduction

Low frequency and low amplitude pulsed electromagnetic field (PEMF) provides many benefits of exercise by activating many of the same cellular second messenger cascades activated by mechanical input (exercise) yet, without imparting a physical stress on the cells. Through a series of *in vitro* and *in vivo* experiments we have shown that at field strengths of 1-2 mT amplitude, this PEMF system stimulates muscle without stressing the tissues and delivers the benefits of slowing muscle loss, improving muscle strength and releasing important myogenic factors. The PEMF leg coil device is designed to provide low amplitude (1.5 mT) magnetic fields for a period of 10 minutes per exposure. The device is tuned and optimised to activate mitochondria in the muscles. Activated muscles are stimulated to produce myogenic factors that are involved in bodily metabolic processes.

1.2. Rationale and justification for the Study

This study is important in looking at how to prevent deconditioning in patients as a result of prolonged bed rest during inpatient hospitalisation.

a. Rationale for the Study Purpose

This study aims to examine a direct benefit of PEMFs on the patient's muscle mass, physical functioning and indirect benefit on the patient's cancer management.

b. Rationale for Doses Selected

Study participants will receive PEMF by alternating between left or right upper thigh, twice per week for 4 consecutive weeks. The recommended doses for this treatment is based on another community study that was already been published by the laboratory [21].

c. Rationale for Study Population

For this study, we would like to validate our hypothesis in haematology patients who required isolated long hospital stays and undergoing induction chemotherapy or stem cell transplant. Healthy volunteer will also be recruited and undergo the same PEMF treatment as the haematology patients. The blood biomarkers from both cohorts will help us assess the direct and indirect benefits of PEMF.

d. Rationale for Study Design

A prospective, double-blinded randomised control study design is the “gold standard” of interventional studies, minimising bias, and ensuring that the effects of the intervention can be accurately evaluated.

2. HYPOTHESIS AND OBJECTIVES

2.1. Hypothesis

The hypothesis for this study is that PEMF can prevent or decrease physical deconditioning by producing myogenic factors that are favourable of muscle proliferation and regeneration, as well as anticancer factors that may help in cancer management.

2.2. Primary Objectives

The objective is to examine if pulsed electromagnetic fields can prevent or decrease physical deconditioning associated with prolonged hospitalisation and immobility of patients by evaluating the changes in muscle secretome at baseline and after exposure to pulsed electromagnetic fields, specifically examining the changes in anticancer factors ceramide, Klotho and HTA1 in patients and healthy volunteers.

2.3. Secondary Objectives

Understanding the blood biomarkers changes in response to PEMF exposure in both cancer and healthy cohorts can help us discover important circulating proteins that may have a role in cancer treatment.

2.4. Potential Risks and benefits:

a. End Points - Efficacy

Patients may require less time for rehabilitation and recovery, reduction in the use of hospital services and lessen economic burdens on them.

Hospital can consider PEMF as part of the cancer treatment regime if prove to be effective in slowing cancer progression. They can become better at utilising the resources to provide service and care for others if this cohort of patients have less demand of the hospital services such as physiotherapy.

b. End Points - Safety

Risks associated with the fields

The risks associated with the application of the fields per se are minimal. We get optimal results with as little as 10 minutes of exposure to PEMFs per week. Since synonymous pathways are activated as by exercise, muscles are only stimulated for as long as the fields are on; PEMF stimulation is as safe as exercise, or possibly even more so as durations of exposure are so brief.

On the other hand, exercise often causes micro-damage to the muscle membrane that must be repaired before physical adaptations can be implemented. Additionally, patient compliance to exercise regimes will be hard to enforce. PEMFs do not impart a physical stress on muscle; that is, PEMFs exert less wear and tear in muscles than exercise.

The non-mechanical attributes of PEMFs pose a benefit here as well. In other words, there would be no overhead to pay, all the gains are directed towards the metabolic and functional adaptations that normally accompany exercise, rather than repairing or replacing damaged muscle – a process that is most notably stymied in the elderly. That is likely the reason that we see such dramatic improvement in metabolic indices with brief PEMFs exposition.

In 2011, we were contacted by the Swiss Health Agency to determine the safety and efficacy of other PEMF-producing apparatuses on the markets. Like ours, none of the commercial apparatuses we tested increases the resting rate of apoptosis or provoked their transformation into a malignant status. Our results agree with the position of the World Health Organization that has deemed fields of this characteristic to be harmless to human health.

World Health Organization: Electromagnetic fields and public health (2007) Exposure to extremely low frequency fields. Accessed 8 April 2024: <https://www.who.int/teams/environment-climate-change-and-health/radiation-and-health/non-ionizing/exposure-to-extremely-low-frequency-field>

The frequency of the applied pulsed is in the extremely low range (non-heating) and the amplitudes are in the 1-3 mT range (3K to 5K smaller than that applied with an MRI). Our PEMF parameters would exert less damage than conventional MRI treatments.

Risks associated with the apparatus

The risk of harm from the PEMF leg coil device is very low as the entire device is completely isolated and grounded to earth. The risk of inductive heating of metallic implants is low since the applied magnetic flux density applied (< 2 mT) is small, and the frequency of the applied field is in the kHz-range. The fields at this frequency and amplitude range will not affect titanium screws and pins. Moreover, as the induced electric field strength is very low (< 1 mV/m), inductive heating of the tissue is very unlikely.

The controls implemented against possible harm to the subject are that the coils are securely enclosed in a poly carbonate case that completely isolates the coils from the user. All electronics are not assessable without completely disassembly of the apparatus with specialised tools. Moreover, any technical malfunction of the control unit of coil setup will result in a leakage current, so that the earth leakage circuit breaker is triggered and the device is powered down, protecting the user.

Finally, the fields are too low strength to cause muscle contraction and accordingly, none have ever been reported. The risk of allergic reaction to the PVC composing the chassis of the coil holding structure is very low.

3. STUDY POPULATION

3.1. List the number of subjects to be enrolled.

36 healthy volunteers age from 30 to 45 will be recruited and randomized to undergo PEMF treatment or no treatment.

3.2. Criteria for Recruitment

Investigational Medicine Unit will look through their database to identify prospective study participants based on the inclusion/exclusion criteria set by the study team. Clinical trial coordinator will contact them to assess their interest in joining the study. Prospective study participants will be given ample time to make the decision. Consent will be obtained from eligible participants in accordance with Singapore Guideline for Good Clinical Practice. Participants who are unable to consent would not be recruited for this study.

3.3. Inclusion Criteria

For inclusion in this study, the following criteria must be fulfilled:

- a. Age between 30-45 years old
- b. Ability to provide informed consent
- c. For healthy volunteer, no prior medical history

3.4. Exclusion Criteria

If subjects meet any of the following criteria, they will be excluded from the trial:

- a. Exercise more than 150 minutes of moderate activity and 45 minutes of vigorous activity per week
- b. Medical history of chronic diseases
- c. On long-term medication/dietary supplementation due to nutritional deficiency
- d. Electronic or electrical metal implants
- e. Existing pregnancy

3.5. Withdrawal Criteria

Study participants will be withdrawn if unexpected adverse events arise through the course of the study. Participants who have missed more than 2 PEMF sessions will be withdrawn.

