3.6. Subject Replacement

Participants withdrawn will be replaced.

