4. TRIAL SCHEDULE

Week	Blood	Treatment Leg 1	Treatment Leg 2	Activity and Diet Questionnaire
1	✓	✓	✓	✓
2		✓	✓	
3		✓	✓	
4		✓	✓	
5	✓			✓
6				
7				
8	✓			✓

Figure 1: The breakdown of the events that will be happening on each week. Blood will be collected on Week 1, 5 and 8 with a set of questions found in the questionnaire will be assessed on Week 1, 5 and 8.

Early Week (Mon/Tue) recruitment					
Mon	Tue	Wed	Thu	Fri	Sat
Leg 1	Leg 1		Leg 2	Leg 2	
Visit 1			Visit 2		

Late Week (Thu/Fri) recruitment					
Thu	Fri	Sat	Sun	Mon	Tue
Leg 1	Leg 1			Leg 2	Leg 2
Visit 1				Visit 2	

Figure 2: The PEMF treatment schedule depending on the recruitment days as a minimum of two days gap is required in between each treatment with alternate legs.

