5.1. Summary of Study Design

Participant will receive either PEMF or no PEMF twice in a week for 4 consecutive weeks. In each week, the participant will place their upper thigh into the PEMF leg coil to receive the treatment. A minimum of two days of rest is required before the next treatment is administered. The participant will also alternate their legs for every treatment session.

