6. METHODS AND ASSESSMENTS

Blood sample collection

Blood from study participants will be collected at Week 1 (before the start of the PEMF treatment as a baseline), Week 5 (one week after completion of 8 sessions of PEMF treatment) and Week 8 (4 weeks after completion of 8 sessions of PEMF treatment). Blood will be collected in EDTA tubes and processed for multiplex and ELISA to assess the blood biomarker levels changes before and after PEMF treatment. Blood collected in normal red serum tubes will be used to assess anticancer potency in human breast cancer cells in vitro.

Activity and Diet Questionnaire

Study participants will be answering a set of questions on the day of blood collection (Week 1, 5 and 8) to help us gain insights about the changes to their daily routine activities or dietary intake which may contribute to the changes in the blood biomarkers levels.

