6.2. Study Visits and Procedures

[figure not shown]

Figure 3: Summary of study visits and procedures

a. Screening Visits and Procedures (Prescreening Visit)

Clinical trial coordinator will perform the recruitment screening. Eligible participants will be recruited and progress to Visit 1.

After participant has given the consent, assign the Subject Randomization ID which can be found on the RFID card.

b. Study Visits and Procedures (Visit 1-10)

Visit 1:

- Activity and diet questionnaire to be completed by the participant
- Blood will be collected from the participant into 2 EDTA tube and 1 red cap tube
- Verify the Subject ID and Randomization ID again before proceeding to use the assigned RFID card to activate the PEMF leg coil

Visit 2-8:

- Verify the Subject ID and Randomization ID again before proceed to use the assigned RFID card to activate the PEMF leg coil

Visit 9:

- Activity and diet questionnaire to be completed by the participant
- Blood will be collected from the participant into 2 EDTA tube and 1 red cap tube (one week after completion of Visit 1-8)

c. Final Study Visit (Visit 10):

Visit 11:

- Activity and diet questionnaire to be completed by the participant
- Blood will be collected from the participant into 2 EDTA tube and 1 red cap tube (four weeks after completion of Visit 1-8)

d. Post Study Follow up and Procedures

Should subjects experience any unlikely discomfort or irritation after treatment, they are free to report it to the study team.

e. Discontinuation Visit and Procedures

Should subjects experience any unlikely discomfort or irritation during treatment or blood collection procedure, they are free to report it to the study team and may ask to stop the treatment. Should subjects are already into the trial for 4 consecutive PEMF therapy (2 weeks, 4 visits), and if withdrawal occurs, subjects are required to return for a final study visit the following week for a final blood withdrawal. No other obligations required.

Subjects may withdraw voluntarily from participation in the study at any time.

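### Randomised participants who miss more than 2 sessions or have an unexpected adverse event are withdrawn and replaced, and their remaining scheduled Week 5 and/or Week 8 blood is not collected

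*Protocol*

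**What the plan says.** The randomisation ID is assigned after consent and before the first session (Protocol 6.2a). Two withdrawal rules in section 3.5 then act on what happens later:

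- On attendance, the rule is "Participants who have missed more than 2 PEMF sessions will be withdrawn".
- On safety, the rule is "Study participants will be withdrawn if unexpected adverse events arise through the course of the study".

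Section 3.6 adds, without conditions, "Participants withdrawn will be replaced".

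The outcome schedule is in section 4: "Blood will be collected on Week 1, 5 and 8". The only rule on blood after withdrawal is in section 6.2e. It opens with a condition, "Should subjects are already into the trial for 4 consecutive PEMF therapy (2 weeks, 4 visits". For those who meet it, the requirement is "if withdrawal occurs, subjects are required to return for a final study visit the following week for a final blood withdrawal"; it then states that nothing more is asked of the participant. No draw is specified for anyone withdrawn before that point. Section 6 dates both later draws from the end of treatment, the last as "Week 8 (4 weeks after completion of 8 sessions of PEMF treatment".

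**The concern.** The primary objective (section 2.2) is change in circulating biomarkers from baseline, and the blood draws are its only data. The protocol ends outcome collection on events that occur after randomisation, then fills the places with new people. What remains is a set of participants who attended well and had no unexpected event.

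If the people lost differ between PEMF and sham, and if being lost is related to biomarker response, the comparison of arms is biased. Section 1.2d justifies the randomised design as a way to minimise bias, and these rules work against that. An analysis plan can choose the analysis set, but it cannot supply samples that were never taken.

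**Working it through.** The protocol gives no power calculation, alpha, SD, effect size or withdrawal rate (section 11.1), so there is no stated figure to reproduce. The check has three parts.

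**1. Which samples are lost**

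*Missed sessions.* There are 8 sessions ("Participant will receive either PEMF or no PEMF twice in a week for 4 consecutive weeks"), and withdrawal comes at the third miss. Listing every attendance history up to the third miss gives C(8,3) = 56. Of these, C(7,3) = 35 have session 1 attended, and so a baseline at Visit 1. What follows depends on how section 6.2e is read:

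| Reading of the condition | Post-baseline draw | No post-baseline draw |
|---|---|---|
| 4 sessions attended in a row | 6 of 35 | 29 of 35 |
| Any 4 sessions attended | 25 of 35 | 10 of 35 |

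Under both readings, all histories with a draw end at session 7 or 8, in Week 4. The draw then falls in Week 5, and Week 8 is lost. If the condition means only that two weeks have elapsed, withdrawals in Week 3 are bled in Week 4, off schedule, and lose both Week 5 and Week 8. **Week 8 is lost in every history under every reading.**

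*Adverse event or voluntary withdrawal.* Right after session 4 (Week 2), the single draw falls at about Week 3, and Weeks 5 and 8 are both lost. Before session 4, no post-baseline draw is required. After the Week 5 draw, that sample is already in hand and only Week 8 is at risk; a withdrawal in Week 7 could still give a draw in Week 8. In Weeks 5 to 8 an unexpected event triggers withdrawal and replacement although no sessions remain.

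**2. How many people (attendance only)**

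Assume independent misses with probability p per session. Then P(withdrawn) = P(Binomial(8, p) ≥ 3).

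| p (assumed) | Withdrawn | Expected of 36 | No post-baseline blood, 4 in a row | No post-baseline blood, any 4 |
|---|---|---|---|---|
| 5% | 0.6% | 0.2 | 84% | 31% |
| 10% | 3.8% | 1.4 | 84% | 33% |
| 15% | 10.5% | 3.8 | 85% | 36% |

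The last two columns are shares of those withdrawn who attended session 1.

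**3. Possible bias**

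Assumptions: 18 per arm (the ratio is not stated), no true effect, lost participants replaced, and a normally distributed tendency to be lost that has correlation ρ with the biomarker response. With loss a on PEMF and b on sham,

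bias = ρ × [φ(z_a)/(1−a) − φ(z_b)/(1−b)],

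where φ is the standard normal density and z_a the normal quantile at a. The term φ(z)/(1−loss) is 0.109 at 5%, 0.195 at 10%, 0.350 at 20% and 0.497 at 30%. The half-width of a 95% interval is t(0.975, 34) × √(2/18) = 2.032 × 0.333 = 0.677 SD. Rejection rates come from a simulated two-sample t-test at a nominal 5%, with 200,000 replicates.

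| Loss, PEMF vs sham | ρ | Bias (SD) | Share of half-width | Rejection rate |
|---|---|---|---|---|
| 20% vs 5% | 0.3 | 0.072 | 11% | 5.6% |
| 20% vs 5% | 0.5 | 0.121 | 18% | 6.6% |
| 30% vs 10% | 0.3 | 0.091 | 13% | 5.8% |
| 30% vs 10% | 0.5 | 0.151 | 22% | 7.5% |
| 20% vs 0% (extreme) | 0.8 | 0.280 | 41% | 13.8% |
| 20% vs 20% | any | 0 | 0% | 5.0% |

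The attendance rates from part 2 in the same formula, with ρ from 0.3 to 0.5, give smaller values: 0.02 to 0.03 SD for 3.8% vs 0.6%, and 0.06 to 0.09 SD for 10.5% vs 0.6%.

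**The case against.** The best reply is about size. Missed sessions alone do not plausibly reach losses of 20% or 30%; under the attendance model that takes a miss rate of about 20% or 24% per session. The rest would have to come from adverse events or voluntary withdrawal, for which the protocol gives no rate. The trial is sham-controlled and double-blind, and section 2.4 describes the fields as too weak to contract muscle, so differential loss is an assumption. Where consent is withdrawn, no protocol rule recovers the blood. This is also an unpowered pilot. All of that stands, and it limits how strongly the point can be put.

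Three further replies carry less weight.

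- The count of 29 of 35 is not a frequency, because the histories are not equally likely and it uses the strictest reading. That is correct. But the looser readings also lose Week 8 every time.
- Section 3.6 does not say that withdrawn participants leave the analysis, and an analysis plan may keep them. It may, but it would have no Week 8 outcome for those withdrawn for missed sessions, and often no post-baseline value at all.
- Figure 1 already sets calendar weeks. It does, but section 6 attaches those weeks to completing 8 sessions, and nothing tells staff to keep withdrawn participants on the Figure 1 schedule. For early withdrawals the loss is inferred from the absence of any required draw, not from a prohibition.

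**Conclusion.** The concern holds. Sections 3.5, 3.6 and 6.2e together remove and replace randomised participants because of events after randomisation, and leave their remaining scheduled primary-outcome blood uncollected. The one narrow exception for Week 8 is an adverse-event withdrawal late enough for the single extra draw to fall in that week.

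The text establishes the loss of samples; the size of any bias is conditional. It is about zero if loss is balanced and acts alike in both arms, 0.07 to 0.15 SD in the moderate unequal scenarios, and 0.28 SD in the extreme one. The loss rates, the correlation and 18 per arm are all assumptions. This should be fixed because the risk is avoidable at low cost and cannot be repaired afterwards. It does not show that randomisation has failed.

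**What to change.** - **Sections 3.5, 3.6 and 6.2e:** separate ending PEMF sessions from leaving the trial, without changing when sessions stop. Unless consent is withdrawn, every randomised participant gives blood and completes the questionnaire at Week 5 and Week 8, whatever the number of sessions attended, so that all can be compared in the assigned arm.
- **Section 6:** count Week 5 and Week 8 from Visit 1, as Figure 1 does, so that the dates exist for people who do not complete 8 sessions.
- **Section 3.6:** treat any further recruits as additional randomised participants, not as substitutes for those withdrawn.

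The cost is an amendment, revised consent wording, and up to two blood visits with assays for each participant who stops sessions. At assumed miss rates of 10% to 15% that is about 1 to 4 people, plus any adverse-event cases. Visits for further recruits come on top. An estimate that keeps everyone in the assigned arm may be slightly smaller than one from completers only. The change must be in place before withdrawals occur.
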